2.8 Handling of Missing, Incomplete, and Repeat Data

Missing Data of Effectiveness Measures

Missing post-injection measurements will not be imputed, whereas missing measurements at the pre-injection of each treatment session will be imputed by the site-specific average of those subjects who receive the treatment at the corresponding treatment session.

Missing Data of Safety Parameters

For safety parameters, missing or invalid data will be treated as missing for the corresponding assessment, except that for partial start dates of adverse events, missing day and month will be imputed to the date of first injection. Completely unknown start dates will be imputed to date of first injection. If day is missing and month and year are present then day is either set to the 1st of the month or the day of the month for the first injection.

Handling of Repeated Data Records

All data records with valid data of efficacy and safety measures are identified for initial and repeat within each study visit and/or assessment time point. Should repeated data records exist within a study visit and/or assessment time point, the initial data record will be utilized for any statistical analyses of the corresponding study visit and/or assessment time point. All existing data records including the repeat data records in the study database will be presented in data listings and CRF data tabulations.

Any resultant incomplete or missing data of either efficacy or safety parameters will be treated as missing in the statistical analyses involving these parameters.

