2.9.1 Effectiveness analysis

As subjects receive multiple single-dose injections, each single-dose injection plus its follow-up period will be considered as a treatment session.

Effectiveness measures obtained over each of the treatment sessions include USFR, CGI-S, CGI-C, DFSS-I, DFSS-S, PGI-S, PGI-C, and DIS at the injection visit (i.e., Day 1, except for CGI-C and PGI-C, and Weeks 13, 26, and 39), 4 weeks post-injection (i.e., Weeks 4, 17, 30, and 43), 8 weeks post-injection (i.e., Week 8, first treatment session only), and 13 weeks post-injection (i.e., Weeks 13, 26, 39, and 52). The injection visit of Day 1 and Weeks 13, 26, and 39 is considered the baseline (or pre-injection), respectively, for each of the consecutive treatment sessions 1 through 4.

For each treatment session, effectiveness analysis of the treatment response will be performed on USFR change from pre-injection, DFSS-I change from pre-injection, and DFSS-S change from pre-injection, CGI-S, CGI-C, PGI-S, PGI-C, and DIS change from pre-injection, at each of the post-injection time points using a t-test.

In addition, the proportion of treatment responders will be reported for the CGI-C and PGI-C at both pre-injection and post-injection time points over each treatment session. Before the analysis, the CGI-C and PGI-C will be dichotomized into 2 categories, with "very much improved" and "much improved" into 1 category and the remaining levels in the other category.

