2.9.2 Safety analysis

Safety measures include adverse events, adverse events of special interest (AESI), dental adverse events (DAE), adverse events associated with distant spread of toxin effect, vital signs and weight, physical exam, neurological exam, dental exam, oral exam, and clinical laboratory tests, as well as lung functioning test for ALS subjects. Adverse events will be coded using the Medical Dictionary for Regulatory Activities (MedDRA) adverse event dictionary.

Like for effectiveness analyses, the baseline for safety analysis includes the pre-injection visits of Day 1, and Weeks 13, 26, and 39, respectively, for each of the treatment sessions 1 through 4.

Drug Exposure

Frequency of drug exposure will be calculated based on the number of injections of study drug administered. Duration of drug exposure will be calculated for each subject for the average duration of individual treatment sessions and total duration of treatment sessions, with the former being the average of the durations of individual treatment sessions the subject has received and the latter being the sum of the durations of individual treatment sessions the subject has received. Duration of drug exposure will be summarized for the safety population as defined in Section 3.1.

Early Termination

Subjects' study disposition will be summarized. A listing will be provided for all early terminations. This listing will include a subject's demographic variables, primary diagnosis, number of injections administered, and the primary reason for early termination.

Adverse Events, AESI, and DAE

All of adverse events will be coded for preferred terminologies using MedDRA. An AE that occurs on the 1st injection date or later will be defined as a TEAE. An AE with start date missing and no valid stop date or stop date being after the first injection date will be considered as a TEAE. TEAEs will be further separated by treatment session.

TEAEs, AESIs, DAEs, and adverse events associated with distant spread of toxin effect will be analyzed by session. Frequency of these types of adverse events will be calculated for each body system (or system organ class, SOC), by preferred term, for number of subjects and proportion reporting the event. The severity of adverse events and the relationship to study medication will be summarized for each body system and preferred term.

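### SAP 2.8 dates undated adverse events to the first injection, which puts them in Session 1 of the by-session safety tables, and it gives no condition for choosing the day when only the day is missing

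*SAP*

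**What the plan says.** **Imputation (SAP 2.8).** Three rules cover incomplete start dates, and the only injection they refer to is the first.
- Start date wholly unknown: "Completely unknown start dates will be imputed to date of first injection".
- Day and month missing: "for partial start dates of adverse events, missing day and month will be imputed to the date of first injection". A recorded year plays no part in this rule.
- Day alone missing: "day is either set to the 1st of the month or the day of the month for the first injection". Nothing says when each option applies.

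**Treatment-emergent status (SAP 2.9.2).** For dated events: "An AE that occurs on the 1st injection date or later will be defined as a TEAE". A separate rule covers missing starts: "An AE with start date missing and no valid stop date or stop date being after the first injection date" also makes the event treatment-emergent.

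**Sessions.** Under SAP 2.9.1, "each single-dose injection plus its follow-up period will be considered as a treatment session". SAP 2.9 allows up to four. SAP 2.9.2 adds that "TEAEs will be further separated by treatment session", and tabulates by body system and "by preferred term, for number of subjects and proportion reporting the event". SAP 5.3 to 5.6 repeat the by-session reporting for treatment-emergent, special-interest, dental and distant-spread events.

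**The concern.** The primary objective (SAP 1.1) is long-term safety and tolerability under repeated injection. The by-session tables are where a change in tolerability from one injection to the next would show. First-injection dating is cautious about whether an event is treatment-emergent, because it keeps the event in. It is not cautious about the session: it raises Session 1 and lowers the later sessions, which can make repeat injections look better tolerated than they were. On the literal text it can also contradict recorded data, since an event recorded only as 2017 in a subject first injected in 2016 would be dated to 2016.

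The missing-day rule raises a different problem. Two programmers could both follow it and produce different tables.

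**Working it through.** The plan has no figure of its own to reproduce on this point. The steps below use the SAP's rules, up to four sessions, and gaps of 13 ± 2 weeks (77, 91 or 105 days). Session is taken as the latest injection on or before the (imputed) start date. The SAP does not state this, but it follows naturally from its session definition.

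**1. Wholly undated events.** Assume onset is equally likely in each of the n sessions received. All such events go to Session 1, so the share in the wrong session is 1 − 1/n:
- n = 1: 0%
- n = 2: 50%
- n = 3: 67%
- n = 4: 75%

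Withdrawals and the optional Sessions 3 and 4 lower the average over subjects.

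**2. Day missing: do the two options agree?** Take a first injection on 20 March 2016 and 13-week gaps, giving re-injections on 19 June, 18 September and 18 December.

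| Recorded month | 1st of month | First-injection day (20th) |
|---|---|---|
| March | before treatment | Session 1 |
| June | Session 1 | Session 2 |
| September | Session 2 | Session 3 |
| December | Session 3 | Session 4 |

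Enumerating every first-injection date in a year and every onset day, with four sessions, the options give a different session or treatment-emergent status for about 25% of onset days at 13-week gaps and about 15% at 11 or 15 weeks.

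**3. Day missing: the natural reading.** This uses the first-injection day in the first-injection month and the 1st of the month elsewhere. An event that follows a re-injection within the same calendar month is then dated before it and goes one session too early; none goes too late. With an average month of 30.5 days, about (30.5 − 1)/2 = 14.75 onset days are affected per re-injection. The share too early is (n − 1) × 14.75 / (n × gap):
- n = 4, 91 days: 3 × 14.75 / 364 = 12% (14% at 77 days, 11% at 105 days)
- n = 3, 91 days: 2 × 14.75 / 273 = 11%
- n = 2, 91 days: 14.75 / 182 = 8%

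The enumeration gives the same values. This assumes uniform onset. If every onset fell within four weeks of an injection, the four-session figure would be about 39%.

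**4. Effect on a by-session table.** The inputs here are assumed, because the documents give neither the number of undated events nor an event rate. Let q be the undated share, L the mean number of events per subject per session (Poisson), and the true rate be flat. A later session keeps a mean of L(1 − q). Session 1 keeps L(1 − q) and gains all nLq undated events, so its mean is L(1 + q(n − 1)). The subject-incidence ratio, later session to Session 1, is

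(1 − exp[−L(1 − q)]) / (1 − exp[−L(1 + q(n − 1))]).

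| n = 4 | q = 0.1% | q = 0.5% | q = 2% | q = 5% |
|---|---|---|---|---|
| L = 1 | 0.998 | 0.989 | 0.956 | 0.897 |
| L = 0.1 | 0.996 | 0.981 | 0.928 | 0.834 |

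For example, at L = 1 and q = 5% the incidences are 61.3% and 68.3%. With two sessions, 2% and 5% undated give 0.977 and 0.943 at L = 1, and 0.963 and 0.909 at L = 0.1.

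**5. Status of an undated event that stopped on or before the first injection.** If the start is imputed first, the dated-event rule in SAP 2.9.2 makes it treatment-emergent. If the missing-start rule is applied to the recorded data first, it is not. The SAP does not give the order.

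**The case against.** The case for leaving the rule alone has substance. Fully dated events do not move, whole-study counts are largely unaffected, and the by-session tables are descriptive. SAP 5.3 lists every treatment-emergent event. Sites are queried on missing data (Protocol 20.1), adverse events are assessed at each visit and call (Protocol 14.8 and Table 2), and special-interest events go to the sponsor within 24 hours (Protocol 16.2.8.1), so that table should rarely be affected. All of this stands, and it limits the size of the effect. It does not supply the missing condition for the day, and it does not justify assigning Session 1 to an event whose session is unknown.

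The percentages in steps 1 to 3 are shares of an unknown and probably small subset. If events cluster in Session 1, fewer undated ones are misplaced. If the year-only rule means filling only the missing parts of the date, there is no net lean with four sessions at 13-week gaps: 28.5% go too early and 27.9% too late. The lean toward Session 1 for year-only dates therefore rests on the literal text.

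A reader might infer that SAP 2.8 and 2.9.2 contradict each other on treatment-emergent status. The documents do not force that. The missing-start rule has a purpose only if it is applied before imputation, and read that way the two sections fit together. The order is unstated, so this is an ambiguity. A reader might also infer that the SAP has no session rule anywhere. That can be said only of the supplied text, which ends before the table and listing shells named in the SAP contents.

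**Conclusion.** The point holds as a should-fix. Following SAP 2.8 as written places undated events, and on the literal text year-only events, in Session 1 whenever they occurred: 0%, 50%, 67% or 75% wrongly for 1 to 4 sessions if onset is equally likely in each. The missing-day rule is not reproducible as written, and its natural reading puts about 12% of day-missing events one session too early with four sessions at 13-week gaps.

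The likely effect is small and is confined to descriptive by-session tables. With four sessions and a flat true rate, the subject-incidence ratio is about 0.98–1.00 if 0.1–0.5% of events are undated and 0.83–0.96 if 2–5% are; all of these shares and rates are assumptions. The documents do not support a stronger claim that the overall safety conclusion is biased or that the higher shares are to be expected.

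**What to change.** Amend SAP 2.8 and 2.9.2 as follows.

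- **(a)** Keep every recorded date part, so that an imputed start never contradicts a known year, month or stop date.
- **(b)** For a missing day, use the first-injection day only in the first-injection month and only for events not known to be pre-dose (Protocol 16.2.1 records pre-dose illness on the same form). Use the 1st of the month otherwise.
- **(c)** Where the known date parts and stop date do not fix the session, keep the event as treatment-emergent under SAP 2.9.2, but show it in a session-unknown row or column of the by-session tables instead of in Session 1.
- **(d)** Report the number of events with imputed start dates per session.
- **(e)** State that the stop-date rule in SAP 2.9.2, applied before imputation, decides treatment-emergent status for undated events.

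A sensitivity table that assigns unresolved events to the most recent compatible injection is optional. It is a bound in the opposite direction, not a better estimate: for wholly undated events with no stop date it uses the last injection, and under equal onset it is wrong for the same 1 − 1/n.

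The cost is a few lines of SAP text and programming, with no new assessments. The downside is a small session-unknown row. It would hold wholly undated events in subjects with more than one session, unless the stop date precedes the second injection. It would also hold day-missing events recorded in a re-injection month, about 24% of day-missing events with four sessions at 13-week gaps (twice the 12% above, since onset is about equally likely on either side of the re-injection). If few dates are incomplete, the count in (d) will show it.

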During the screening period, the following will be assessed to evaluate the subject's eligibility to participate in the study: inclusion and exclusion criteria; medical, surgical, and medication history; presence or prior history of aspiration, aspiration pneumonia, choking, and/or dysphagia; complete physical exam (including vital signs, height, and weight); neurologic exam; dental exam; clinical laboratory testing; urine pregnancy testing (females of childbearing potential only); and forced vital capacity (FVC) (if warranted, such as in ALS patients). All subjects successfully completing screening will have the following procedures/assessments conducted at baseline (Day 1) before the first injection of MYOBLOC: brief physical exam (including vital signs); FVC (if warranted); neurologic exam; Columbia Suicide Severity Rate Scale (C-SSRS); oral exam; saliva production quantitatively determined via USFR; qualitative assessments by the Investigator including CGI-S and DFSS-I; subject assessments including PGI-S, DFSS, DIS; and urine pregnancy test (result must be negative to proceed with the injection). Those subjects who satisfy all eligibility criteria may receive a dose of MYOBLOC (3,500 Units) via injections into the submandibular and parotid glands on Day 1. Subjects will be contacted by telephone 24 hours post-injection to inquire about their health status.

Subsequent study visits will occur at Weeks 4 (± 3 days), 8 (± 3 days), 13 (± 2 weeks), 17 (± 5 days), 26 (± 2 weeks), 30 (± 5 days), 39 (± 2 weeks), 43 (± 5 days), and 52 (± 2 weeks), with safety and effectiveness assessments made as detailed in the Schedule of Assessments in Table 2 in Section 14.1; telephone follow up will be done at Weeks 14 (± 1 day), 21 (± 5 days), 27 (± 1 day), 34 (± 5 days), 40 (± 1 day), and 47 (± 5 days)

Injections at each treatment session will be done when the subject returns to baseline status as determined by the Principal Investigator, with a minimum interval of 11 weeks from the prior injection but no later than 15 weeks from the prior injection. If after the first treatment of 3,500 Units the subject develops intolerable side effects, but still wishes to remain in the

study, the Investigator has the discretion to decrease subsequent doses, but to no less than a total dose of 2,500 Units.

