13.2 Study Drug Administration and Compliance

Subjects will receive single dose injections of MYOBLOC every 13 weeks (± 2 weeks) for a maximum total of 4 treatments. MYOBLOC will be injected first into the submandibular glands (right and then left) followed by the parotid glands (right and then left)

- Total dose of 3,500 Units (0.7 mL) of MYOBLOC with 1,500 Units (0.3 mL) injected into each parotid gland and 250 Units (0.05 mL) injected into each submandibular gland.

Subsequent injections at each treatment session will be done when subjects return to baseline status as determined by the Investigator, with a minimum interval of 11 weeks from the prior injection. Study drug injections should not be administered if an adverse event of dysphagia or dry mouth of moderate to severe severity persists without prior consultation with the Medical Monitor. If the adverse event has not resolved or has not improved to a mild severity by the end of the per protocol window for injections to occur (every 13 ± 2 weeks), the Medical Monitor should be contacted to discuss whether or not the subject should be dosed, discontinued, etc.

If after the first treatment of 3,500 Units the subject develops intolerable side effects, but still wishes to remain in the study, the Investigator has the discretion to decrease subsequent doses, but to no less than a total dose of 2,500 Units. If this does occur, the total dose can therefore be 2,500 Units to 3,500 Units of MYOBLOC. The Investigator must clearly indicate the adjusted dose given. MYOBLOC will be injected first into the submandibular glands (right then left) followed by the parotid glands (right then left) as follows:

- Total dose of 2,500 to 3,500 Units (0.5 mL to 0.7 mL) of MYOBLOC with 1,000 to 1,500 Units (0.2 mL to 0.3 mL) injected equally into each parotid gland and 250 Units (0.05 mL) injected into each submandibular gland.

All MYOBLOC injections will be performed by Investigators who have prior experience or have been appropriately trained with injecting botulinum toxin and such experience/training will be documented in the study records. Injections will be guided by external anatomical landmarks or by external anatomical landmarks with ultrasound-guided confirmation (Appendix A). Sites designated as “ultrasound” sites will perform all their injections with ultrasound-guidance.

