- DFSS-S – site personnel will teach the subject how to use the subject diary to complete the DFSS and the subject will perform a practice entry at this visit, with the first real entry to occur that evening.

Once all assessments have been completed, evaluated, and eligibility confirmed, the subject will receive a dose of MYOBLOC via injections into the submandibular and parotid glands as detailed in Section 13.2. Subjects will be contacted by telephone 24 hours (± 1 day) post-injection to inquire about their health status and to remind the subject to complete their diary.

14.3.2 Weeks 4, 8, and 13

Subjects will return to the clinic for follow-up assessments/procedures at Weeks 4, 8, and 13. Visit windows are provided to allow flexibility in scheduling subjects for appointments: Weeks 4 and 8 have a ± 3 day window and Week 13 has a ± 2 week window. The following assessments will be completed at each study visit unless otherwise specified:

- Complete (Weeks 4 and 13) and brief (Week 8) physical exam (including vital signs and weight);
- FVC in all subjects with ALS, and other subjects if done at screening, at Weeks 4 and 13 and as needed, per Investigator discretion, at Week 8;
- Clinical laboratory tests (fasting), including full chemistry panel (including glucose and alkaline phosphatase), hematology, and urinalysis at Week 13 and as needed, per Investigator discretion, at Weeks 4 and 8;
- Urine pregnancy test (as clinically warranted);
- Neurologic exam at Week 13 and as clinically warranted at Weeks 4 and 8;

- Dental exam by a licensed dentist at Weeks 4 and 13, and as clinically warranted based on predefined safety criteria;
- Oral exam by Investigator (Week 8);
- Evaluation of adverse events;
- C-SSRS Since Last Visit version;
- Review of concomitant medications;
- Review of subject diary;
- CGI-S and CGI-C (Assessor) before USFR;
- USFR collection;
- DFSS-I;
- PGI-S and PGI-C (Subject);
- DIS (Subject); and
- DFSS-S via entry in the subject's diary, not during study visit, daily for first 2 weeks after injection of MYOBLOC and then weekly for remainder of treatment session.

14.4 Treatment Session 2

14.4.1 Day 1

On Day 1 of treatment session 2 (same day as Week 13 visit), subjects may receive MYOBLOC (as detailed in Section 13.2) after all 13-week assessments have been completed for the prior treatment session.

14.4.2 Weeks 14, 17, 21, and 26

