17.6 Safety Endpoints

Safety endpoints include adverse events and AESI, vital signs and weight, neurological exam, physical examination, dental exam, C-SSRS, and clinical laboratory tests. Adverse events will be coded using the Medical Dictionary for Regulatory Activities (MedDRA) adverse event dictionary.

For safety endpoints, records with valid data within each visit or assessment time point will be identified for initial and repeat, where applicable. The initial record will be used in statistical analysis, whereas all records will be presented in data listings. Missing or invalid data will be treated as missing for the corresponding visit or time point.

The baseline of each treatment session consists of the corresponding measurement value obtained at pre-injection of each treatment session (i.e., Day 1, Weeks 13, 26, and 39).

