2.6.1 Effectiveness measures

Several effectiveness measures are assessed over each of the treatment Sessions 1 through 4 at the injection visit (i.e., Day 1, and Weeks 13, 26, and 39), 4 weeks post-injection (i.e., Weeks 4, 17, 30, and 43), 8 weeks post-injection (i.e., Week 8, first treatment session only), and 13 weeks post-injection (i.e., Weeks 13, 26, 39, and 52). Where applicable, the measurement value obtained at pre-injection of each treatment session (i.e., Day 1 and Weeks 13, 26, and 39 for each of the 4 treatment sessions, respectively) is defined as the baseline of the corresponding measures. For the CGI-C and PGI-C, the corresponding severity score observed at pre-injection of each treatment session will be used as the baseline measurement of the corresponding session in analysis.

Unstimulated Salivary Flow Rate (USFR)

The USFR (g/minute) is the salivary flow rate assessed by the independent assessor in an unstimulated state (i.e., at least 1 hour postprandial) at screening, just before the first injection of study drug (Day 1) to establish a baseline salivary flow rate, and at each subsequent study visit (Appendix B of the protocol). To determine USFR at each study

visit, saliva will be collected over a 5-minute collection period using weighing cups

hey will be asked to expectorate, as needed, any saliva that accumulates in their mouth into the pre-weighed cup during the 5-minute collection period.

Although not a rating scale, the same person should conduct this assessment throughout the study to minimize collection technique bias.

Clinical Global Impression of Severity (CGI-S) and Change (CGI-C)

The CGI-S scale is used to record the severity of illness (sialorrhea) on Day 1 (i.e., study baseline) before the first injection of study drug, at each subsequent study visit or, if applicable, at discontinuation from the study. CGI-S will be assessed by a trained assessor on a 7-point scale ranging from “normal” to “among the most extremely ill patients” (Appendix C of the protocol). The CGI-C, used to record change or improvement in illness from baseline (i.e., pre-injection) of each treatment session, will be assessed at each study visit after Day 1 by the assessor on a 7-point scale ranging from “very much improved” to “very much worse” (Appendix C of the protocol). Both CGI scales will be completed independent of the subject’s self-assessment (PGI-S and PGI-C) so neither party knows how the other has rated the scales.

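### The SAP's first-record rule has no exception for session baselines, so if a subject is assessed, deferred and re-assessed within one visit window, the baseline for Sessions 2 to 4 can be a value taken up to 4 weeks before the injection

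*SAP*

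**What the plan says.** **Repeat records.** SAP 2.8 covers efficacy and safety measures alike. Records are "identified for initial and repeat within each study visit and/or assessment time point", and where there is more than one, "the initial data record will be utilized for any statistical analyses of the corresponding study visit and/or assessment time point". All records go into the listings. Protocol 17.6 has a similar rule, for safety endpoints only: "The initial record will be used in statistical analysis, whereas all records will be presented in data listings".

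**Baseline.** SAP 2.6.1 defines the session baseline as "the measurement value obtained at pre-injection of each treatment session". SAP 2.9.1 identifies it with the injection visit (Day 1, Weeks 13, 26 and 39), and SAP 2.9.2 carries this over to safety. None of these sections says that the last value before the injection is used, and none says whether it overrides SAP 2.8.

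**Visits and re-injection.** Protocol 14.3.2 states that "Week 13 has a ± 2 week window"; Weeks 26 and 39 have the same width. The notes to the schedule of assessments make each of these visits both the last of one session and the first of the next, with injection after the assessments. Protocol 10 makes re-injection depend on the investigator's judgement that baseline status has returned. Its limits on timing read: "with a minimum interval of 11 weeks from the prior injection but no later than 15 weeks from the prior injection". Protocol 13.2 repeats the return-to-baseline condition. It also holds back injection while moderate to severe dysphagia or dry mouth persists, unless the Medical Monitor has been consulted.

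**The concern.** The design gives two reasons why an injection may not follow the first assessment in the window: the subject has not returned to baseline status, or an adverse event of the named kind persists. If the assessments are then repeated on the later injection day and filed under the same visit, that visit holds two records. The value wanted as baseline for the next session is the later one, and the repeat-record rule points to the earlier one.

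At stake is the change from pre-injection in Sessions 2 to 4 for USFR, DFSS-I, CGI-S, PGI-S and DIS (SAP 4.4), which serves the secondary objective on magnitude of response to repeat dosing. A baseline taken during residual benefit leaves less room for the next injection to show a change, and it would do so selectively in subjects whose response lasts longest. The same early record, used as the 13-week outcome of the preceding session, would make that session look better. Session changes in vital signs, weight and C-SSRS follow the same rule, though they are summarised descriptively and no direction can be given for them.

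**Working it through.** **Step 1: the plan's own window.** From 13 ± 2 weeks: 13 − 2 = 11 and 13 + 2 = 15. This reproduces the limits in Protocol 10.

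**Step 2: longest lag from initial record to injection.** The lag is the injection week minus the week of first assessment. With injection at Week 15:

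| First assessed (week) | Longest lag (weeks) |
|---|---|
| 11 | 4 |
| 12 | 3 |
| 13 | 2 |
| 14 | 1 |
| 15 | 0 |

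Under a last-record-before-injection rule, with assessments repeated on the injection day, every entry becomes 0.

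The 4-week ceiling rests on the 15-week limit in Protocol 10. The synopsis and Protocol 13.2 give the ±2-week interval, but their return-to-baseline sentence states only the 11-week minimum. Protocol 13.2 also leaves an adverse event that persists at the end of the window to discussion with the Medical Monitor. These passages must be reconciled. If an injection fell at Week 16 or 17, the lag from Week 11 would be 5 or 6 weeks.

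**Step 3: when the lag comes from the first-record rule.**

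- The whole visit moves to the injection day: one record, lag 0, no problem.
- Assessed early and nothing repeated: the early record is the only one. The baseline is stale, but SAP 2.8 is not the cause and changing it would not help.
- Assessed early and re-assessed at injection under the same visit label: two records, and SAP 2.8 read literally selects the earlier.

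Only the third path produces the conflict.

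**Step 4: illustrative size in one affected subject.** The documents give no decay curve. *Assumption:* the effect declines linearly from its peak at Week 4 to zero at Week 15, a span of 11 weeks. Residual effect at week t is (15 − t)/11 of peak:

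- Week 11: 4/11 = 36%
- Week 12: 3/11 = 27%
- Week 13: 2/11 = 18%
- Week 14: 1/11 = 9%

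If the record is taken at week t and the injection given at week u (u at most 15), the next session's change is understated by (u − t)/11 of peak. That is about 9% per week of deferral: 9% for Week 11 to 12 or 14 to 15, 18% for Week 11 to 13, and 36% for Week 11 to 15.

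**The case against.** The strongest objection is that neither document describes the triggering event. Protocol 14.4.1, 14.5.1 and 14.6.1 place the injection on the same day as the Week 13, 26 or 39 visit. No deferral visit or repeat battery is mentioned, and the wide window allows the whole visit to move. This stands: the problem is conditional, and the documents do not show that it occurred.

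Second, a visit without an injection is not naturally an injection visit, so the specific definition of baseline may be read as governing the general repeat rule. That reading is reasonable, but the SAP does not state it, and SAP 2.8 applies to any analysis of the visit. What remains is an unresolved conflict. A reader might infer that the SAP certainly uses the wrong value; the text supports only that it can.

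Third, a reader might infer that every deferred subject is still improved at the first record. That follows when deferral is for not having returned to baseline status. It does not follow when the reason is persisting dysphagia or dry mouth, where the direction of any bias is not established.

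Fourth, a reader might multiply the per-subject figure by a deferral share to get a bias in the pooled mean. With an assumed 10% to 40% deferred, the product runs from 0.10 × 9.1% = 0.9% to 0.40 × 36.4% = 14.5% of peak. The documents give no deferral share. The assumed curve also reaches zero only at Week 15, which would imply far more deferral than that. These products are not an estimate.

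Finally, the reach is limited. Session 1's baseline is unaffected. CGI-C and PGI-C are rated directly as change, so their post-injection ratings and responder proportions subtract no baseline record. DFSS-S comes from the diary rather than the visit, so the mechanism applies to it less clearly. Effectiveness is the secondary objective, and repeated records will be visible in the listings.

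**Conclusion.** The point holds in conditional form. A stated rule can select a value that contradicts the SAP's own definition of baseline, and the SAP does not say which prevails. The age of that value is bounded at 15 − 11 = 4 weeks under Protocol 10.

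It requires that a subject be assessed, deferred and re-assessed under one visit label. Where the deferral was for not having returned to baseline, the Session 2 to 4 change from pre-injection would tend to be understated. The size is unknown; the figure of about 9% of peak per week of deferral, up to 36% in an affected subject, rests wholly on the assumed linear decline. For effectiveness, the rule comes from SAP 2.8 alone, because Protocol 17.6 applies it only to safety endpoints.

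This should be corrected because the remedy is simple and costs almost nothing. It does not threaten the primary safety objective.

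**What to change.** - In SAP 2.8, add: *The baseline of each treatment session is the last valid record on or before the injection that opens the session; this overrides the initial-record rule.*
- In Protocol 17.6, make the same exception for session baselines of the safety endpoints.
- State which record serves as the 13-week outcome of the preceding session when there are two, since the initial record may be the more favourable one.
- Report the number of sessions with repeated pre-injection records, so that the reader can see whether the issue arose.

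The cost is a few sentences and one derivation rule. No new data are needed, because all repeat records are already kept and listed. If no session has repeated records, the results do not change.
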